#### **6.2.2.6. Duration of complete response (Cohort A only)**

Duration of complete response (DoCR) will be analyzed for participants with CIS at randomization.

DoCR is defined as the time from the first documentation of CR to the date of an EFS event for participants with CR.

For participants without an EFS event, DoCR will be censored according to the rules in Table 17

$$\text{DoCR (months)} = [\text{date of event or censoring} - \text{first date of CR} + 1]/30.4375$$

**Table 17. Outcome and Event Dates for DoCR Analyses**

Scenario	Date of event/censoring	Outcome
Event - After at most one missing or inadequate post-baseline disease assessment, OR - $\leq 24$ weeks after the 'start date')	Date of event	Event
Event - After 2 or more missing or inadequate post-baseline disease assessments	Date of last adequate disease assessment documenting no event	Censored
No Event	Date of last adequate disease assessment documenting no event	Censored

Kaplan-Meier estimates (product-limit estimates) will be presented by treatment arm for Cohort A together with a summary of associated statistics including the median DoCR time with 2-sided 95% CIs. In particular, the DoCR rates at 6, 12, 18, 24, 30, 36, 42, and 48 months will be estimated with corresponding 2-sided 95% CIs. The CIs for the median will be calculated according to Brookmeyer and Crowley (1982) and the CIs for the survival function estimates at the time points defined above will be derived using the log-log transformation according to Kalbfleisch and Prentice (2002) (conftype=loglog default option in SAS Proc LIFETEST) with back transformation to a CI on the untransformed scale. The estimate of the standard error will be computed using Greenwood's formula.

Frequency (number and percentage) of participants with each event type (progression of disease, recurrence of high-grade disease, or death) and censoring reasons will be presented by treatment arm for Cohort A. Reasons for censoring will be summarized according to the categories in Table 18 following the hierarchy shown.

**Table 18. DoCR Censoring Reasons and Hierarchy**

Hierarchy	Condition	Censoring Reason
1	Event after 2 or more missing or inadequate post-baseline disease assessments	Event after 2 or more missing assessments
2	No event and [withdrawal of consent date $\geq$ 'start date']	Withdrawal of consent
3	No event and lost to follow-up in any disposition page	Lost-to-follow-up
4	No event and none of the conditions in the prior hierarchy are met	Ongoing without an event

The DoCR time or censoring time and the reasons for censoring will also be presented in a participant listing.

### **DoCR (Alternative Definition): Includes all randomized participants (Cohort A only)**

Rather than limiting the analyses of DoCR to the subset of participants with CR, statistical inference on DoCR can be performed including all randomized participants with CIS at randomization based on the restricted mean methodology [(Huang et al, Annals of Internal Medicine, 2020) and (Huang et al, JAMA Oncology, 2018)].

DoCR is defined as EFS time minus P/D/R event-free time at cut-off time  $\tau$ .

$$\text{DoCR} = \text{EFS Time} - (\text{P/D/R}) \text{ event-free time, at cutoff time } \tau.$$

where P/D/R is a composite endpoint of PD (EFS event), Death, or CR whichever occurs first. The cut-off time  $\tau$  is intended to reflect the time point in the Kaplan-Meier curve beyond which there are no meaningful information on EFS or P/D/R event-free time.

Specifically,

- DoCR = Date of P/D or Censoring Date – Date of CR, for responders whose EFS time  $\leq$  cutoff time  $\tau$ .
- DoCR = Randomization date + cutoff time  $\tau$  – Date of CR, for responders whose EFS time  $>$  cutoff time  $\tau$ .
- DoCR = 0, for non-responders before cutoff time  $\tau$ .

where P/D stands for progression or death.

The mean DoCR is the area between the EFS curve and the P/D/R event-free curve in  $(0, \tau)$ .

The principle of selecting the truncation cutoff time  $\tau$  for mean DoCR is that we can make a valid inference for the area under the curve with respect to the P/D/R and P/D events. There are 3 cases for the selection in a single arm:

1. If the estimated P/D/R event-free curve has not reached 0 on the basis of the observed data (that is, the largest observed time to P/D/R or censoring is not a P/D/R event time), the truncation time for mean DoCR can be as large as the largest observed time to P/D/R or censoring.
2. If the estimated P/D/R event-free curve has reached 0 but the estimated P/D event-free curve has not reached 0 on the basis of observed data (that is, the largest observed time to P/D/R or censoring is a P/D/R event time, but the largest observed time to P/D or censoring is not a P/D event time), then the truncation time for mean DoCR can be as large as the largest observed time to P/D or censoring.
3. If both estimated event-free curves have reached 0 on the basis of observed data (that is, the largest observed time to P/D or censoring is a P/D event time), there is no restriction in selecting the truncation time point for mean DoCR.

After selecting the truncation cutoff time  $\tau$  for each arm following the steps above, the truncation cutoff time in the 2-arm comparison is determined as follows:

1. If both the EFS curve and the P/D/R event-free curve crossed zero for both arms, use the maximum of the  $\tau$  for each of the arms;
2. Else if both the EFS curve and the P/D/R event-free curve crossed zero for Arm A, then use the  $\tau$  of Arm B;
3. Else if both the EFS curve and the P/D/R event-free curve crossed zero for Arm B, then use the  $\tau$  of Arm A;
4. Else use the minimum of the  $\tau$  for each of the arms

DoCR for each treatment arm will be displayed graphically and between treatment arms can also be compared using RMST methodology (see [Section 6.2.2.3](#)). The variance of the mean DoCR can be derived by bootstrapping or analytically based on counting process theory.

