### BCG Naïve Cohort (Cohort A)

- Arm A: PF-06801591 + BCG (IND and MNT)
- Arm B: PF-06801591 + BCG (IND only)
- Arm C: BCG only (IND and MNT)

where IND=induction and MNT=maintenance

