In particular, as it pertains to the **cut-off point ( $\tau$ )** to evaluate the RMST, it is noted that the cut-off point should not exceed the minimum of the largest observed time for both treatment arms so that the RMST of all treatment arms being evaluated can be adequately estimated and comparison between treatments is feasible;  $\tau$  should be clinically meaningful and closer to the end of the study follow-up so that the majority of survival outcomes will be covered by the time interval. The RMST up to time  $\tau$  can then be interpreted as the expected survival time restricted to the common follow-up time  $\tau$  among all participants. To avoid arbitrary selection of the common cut-off  $\tau$  for both treatment arms,  $\tau$  is pre-specified as:

$\tau$  = minimum of (largest observed EFS time for the experimental arm, largest observed EFS time for the control arm).

The treatment effect between the experimental arm and the control arm will be assessed based on the difference in RMST. The associated 95% CI for the difference in means and 1-sided p-value will be generated.

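### Two of the four truncation-time rules for the two-arm mean DoCR comparison name Arms A and B, both experimental, and never the control Arm C

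*SAP*

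**What the plan says.** The alternative DoCR definition in SAP 6.2.2.6 first gives each arm its own cut-off τ. It then says "the truncation cutoff time in the 2-arm comparison is determined as follows" and lists four ordered branches:

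1. "If both the EFS curve and the P/D/R event-free curve crossed zero for both arms": take the larger of the two cut-offs.
2. "Else if both the EFS curve and the P/D/R event-free curve crossed zero for Arm A": take the τ of Arm B.
3. "Else if both the EFS curve and the P/D/R event-free curve crossed zero for Arm B": take the τ of Arm A.
4. "Else use the minimum of the" cut-offs of the two arms.

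P/D/R is the composite of EFS event, death or complete response. The section adds that DoCR "between treatment arms can also be compared using RMST methodology" and refers to SAP 6.2.2.3 for the method. That section is written for one experimental arm against the control: "The treatment effect between the experimental arm and the control arm will be assessed based on the difference in RMST". SAP 2.2 and 5.2 define Arm A and Arm B as the two sasanlimab-plus-BCG arms and Arm C as BCG alone. SAP 6.2.2.5 compares complete response in the same CIS participants as each of Arms A and B against Arm C.

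**The concern.** The comparisons that matter in Cohort A are A vs C and B vs C. A rule that swaps cut-offs between A and B cannot be applied to either pair when its branch 2 or 3 is reached. The truncation time could then come from an arm outside the comparison. If that time runs past the last observation in Arm C while Arm C's curve is still above zero, Arm C's restricted mean is not estimable without extrapolation. If it is shorter, usable data are discarded. The programmer would in practice have to settle τ after seeing the curves. SAP 6.2.2.3 pre-specifies τ for EFS to avoid that kind of arbitrary choice. The main DoCR analysis is Kaplan-Meier by arm with no between-arm test, so the alternative definition is the only DoCR analysis that offers a comparison of arms.

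**Working it through.** The documents give no value of τ or of mean DoCR, so there is no stated figure to reproduce. The check traces the branches and then asks how often each would be reached.

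**Trace for A vs C**

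| Arms of the pair whose curves reach zero | Rule as written | Cut-off by the rule's own logic |
|---|---|---|
| Both | Branch 1: maximum over A and C | Same |
| Neither | Branch 4: minimum over A and C | Same |
| A only | Branch 2: τ of B | τ of C |
| C only | No branch names C; falls to branch 4, the minimum | τ of A |

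In the C-only row the minimum is not well defined, because the single-arm rules place no restriction on τ once both of an arm's curves have reached zero. If C's τ is treated as unlimited, the minimum is A's τ, which is the right answer. If C's last observed time is used, the result is the same or shorter, and still estimable.

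There is a further literal problem if Arm B is read into A vs C. When B's curves reach zero and A's do not, branch 3 assigns A's τ without checking Arm C.

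B vs C mirrors all of this: B only takes the τ of A, C only has no branch, and A's curves could trigger branch 2.

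**How often each case arises for A vs C**

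Inputs from the SAP:
- Median EFS 24 months (Arm C) and 34.8 months (Arms A and B), exponential, from 5.1.1. Monthly hazards are ln 2/24 = 0.0289 and ln 2/34.8 = 0.0199.
- EFS drop-out 20% per arm (5.1.1).
- Accrual over 22 months (5.1.1).
- Follow-up of 36 months after the last randomisation (5.1.2; the power assumptions in 5.1.1 use about 33).
- At least 250 participants with CIS, so 250/3 ≈ 83 per arm.

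Assumptions added: uniform accrual, because the SAP calls it non-uniform without giving the shape; drop-out spread exponentially over 36 months, hazard −ln(0.80)/36 = 0.0062; and the Cohort A medians applied to participants with CIS.

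An arm's EFS curve reaches zero when its largest observed EFS time is an event. Each scenario had 2,000 simulated trials, with event times either continuous or placed on the 12-weekly then 24-weekly visit schedule (shown as continuous / schedule):

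| Medians C / A (months) | Both | A only | C only | Neither | Exactly one |
|---|---|---|---|---|---|
| 24 / 34.8 (SAP) | 0.25% / 0.15% | 2.2% / 1.8% | 4.5% / 4.85% | 93.05% / 93.2% | 6.7% / 6.65% |
| 12 / 17.4 (assumed) | 2.15% / 2.2% | 7.7% / 8.45% | 19.25% / 18.6% | 70.9% / 70.75% | 26.95% / 27.05% |
| 6 / 8.7 (assumed) | 30.4% / 26.65% | 10.5% / 13.7% | 42.8% / 40.2% | 16.3% / 19.45% | 53.3% / 53.9% |

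Branches 2 and 3 also require the P/D/R curve to reach zero, which the simulation did not model. A strict ceiling on exactly one arm qualifying is therefore 1 minus the neither column. Under the SAP medians that is 1 − 0.9305 = 6.95%, still about 7%. Under the two assumed scenarios it is about 29% and about 81% to 84%.

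Arm B has the same assumed median as Arm A, so its EFS curve reaches zero in about 2.2% + 0.25% = 2.45% of trials (1.8% + 0.15% = 1.95% on the visit schedule). That bounds the further branch 3 problem under the SAP medians.

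**The case against.** A reader might infer that the A vs C and B vs C comparisons take their cut-off from the wrong pair in general, as if branch 4 meant the minimum over Arms A and B. The text does not support that. Branches 1 and 4 speak of both arms, or of each of the arms, within a two-arm comparison, and give the right pair whichever two arms are compared. Branch 4 applies to A vs C in about 93% of trials simulated under the SAP's medians.

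It can also be said that Arm A and Arm B are generic labels in borrowed wording, and that the surrounding text makes the intended pair plain. That is a plausible origin, and the neighbouring sections do point to experimental against control. But the SAP nowhere says that the labels are generic here, and everywhere else it uses them for two specific arms.

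The limited stakes are a fair objection and stand. The SAP says that this inference can be performed, not that it will be. It is an alternative definition of a secondary endpoint that is not a key one, with no alpha attached. EFS, OS and the Kaplan-Meier DoCR analysis do not depend on it. SAP section 2 also reports that pooled EFS events are accruing much more slowly than projected, which makes curves that reach zero less likely.

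**Conclusion.** The rule is wrong as written in branches 2 and 3 and correct in branches 1 and 4. When only Arm A's curves reach zero, A vs C is sent to Arm B's cut-off; when only Arm B's do, B vs C is sent to Arm A's; and Arm C alone reaching zero has no branch. Under the SAP's medians, exactly one arm of A vs C reaches zero in at most about 7% of simulated trials. The clearly misdirected case, Arm A only, is about 2%, and the uncovered case, Arm C only, is about 5%. These figures rest on exponential EFS, uniform accrual, about 83 participants with CIS per arm and the Cohort A medians holding in CIS. If CIS medians were half or a quarter as long, the EFS curve of exactly one arm would reach zero in about 27% or about 53% to 54%, but the documents give no CIS-specific median. This is a minor point about pre-specification and does not threaten the trial's conclusions.

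**What to change.** In SAP 6.2.2.6, in branches 2 and 3 only, replace Arm A with the experimental arm and Arm B with the control arm (Arm C). State that the rule is applied separately to A vs C and to B vs C. Branches 1 and 4 stay as they are.

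A vs C then uses only the cut-offs of A and C, and B vs C only those of B and C. Arm C alone reaching zero is covered by branch 3. The change aligns the pair of arms with SAP 6.2.2.3; it does not adopt that section's formula for τ, which is the minimum of the two largest observed times. The cost is a wording change in the SAP, with no new data.

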#### **6.2.2.7. Event-free survival (Cohort B1)**

In Cohort B1, cytology, cystoscopy, and biopsy (as clinically indicated) will be required every 12 weeks for 2 years following date of first dose until first occurrence of progression of disease, recurrence of high-grade disease, or persistence of CIS (for participants with CIS at baseline) regardless of initiation of subsequent anti-cancer therapy. In addition, disease status will be assessed through imaging in the case of a positive cytology or cystoscopy and at screening, every 24 weeks for 2 years after initiation of study intervention until first occurrence of progression of disease, recurrence of high-grade disease, persistence of CIS regardless of initiation of subsequent anti-cancer therapy, or EOT.

EFS is defined as the time from first dose until progression of disease, recurrence of high-grade disease, persistence of CIS, or death due to any cause, whichever occurs first.

The censoring and event date options to be considered for the EFS analysis are presented in Table 14. An event is as defined in Table 19.

**Table 19. Possible Clinical Outcomes for Participants With CIS at baseline and EFS Evaluation**

Population	Disease Assessment	EFS Event Y/N
Participants with CIS at baseline	Progressive disease [a] before achieving a CR for participants with CIS only at baseline	Y
	Progressive disease after achieving a CR	Y
	Recurrence of high-grade disease before achieving a CR for participants with CIS and concurrent papillary disease at baseline	Y
	Recurrence of high-grade disease after achieving a CR	Y
	Persistence of CIS (non-CR)	Y
	Recurrence of low-grade disease	N

[a] Including appearance of new high-grade Ta or T1 disease

EFS (months) = [date of event or censoring – date of first dose+1]/30.4375

An EFS listing only will be provided by investigator assessments.

#### 6.2.2.8. Time to recurrence of low-grade disease (Cohort A only)

Time to recurrence of low-grade disease is defined as the time from randomization to the date of first documentation of recurrence of low-grade Ta disease, according to the “Oncology Biopsy” CRF page.

For participants without an event (recurrence of low-grade Ta), time to recurrence of low-grade disease will be censored according to the rules in Table 20.

**Table 20. Outcome and Event Dates for the Analysis of Time to Recurrence of Low-Grade Disease**

Scenario	Date of event/censoring	Outcome
No adequate baseline assessment	Date of randomization	Censored
Event - After at most one missing or inadequate post-baseline disease assessment, OR - ≤ 24 weeks after the date of randomization	Date of event	Event
Event - After 2 or more missing or inadequate post-baseline disease assessments	Date of last adequate disease assessment documenting no event	Censored
No event	Date of last adequate disease assessment documenting no event	Censored

The treatment effect will be estimated using a Cox's Proportional Hazard model stratified by randomization strata to calculate the hazard ratio for time to recurrence of low-grade disease between each experimental arm and Arm C.

Time to recurrence of low-grade disease will be analyzed using Kaplan-Meier methods. Kaplan-Meier estimates (product-limit estimates) will be presented by treatment arm together with a summary of associated statistics including the median time to recurrence of low-grade disease with 2-sided 95% CIs. Time to recurrence of low-grade disease rates at 6, 12, 18, 24, 30, 36, 42, and 48 months will be estimated with corresponding 2-sided 95% CIs. The CIs for the median will be calculated according to Brookmeyer and Crowley (1982) and the CIs for the survival function estimates at specific time points will be derived using the log-log transformation according to Kalbfleisch and Prentice (2002) (with back transformation to a CI on the untransformed scale). The estimate of the standard error will be computed using Greenwood's formula. A Kaplan-Meier plot for time to recurrence of low-grade disease will be generated.

Reasons for censoring will be summarized according to the categories in Table 21 following the hierarchy shown.

**Table 21. Time to Recurrence of Low-Grade Disease Censoring Reasons and Hierarchy**

Hierarchy	Condition	Censoring Reason
1	No adequate baseline assessment	No adequate baseline assessment
2	Event after 2 or more missing or inadequate post-baseline disease assessments	Event after 2 or more missing assessments
3	No event and [withdrawal of consent date $\geq$ date of randomization]	Withdrawal of consent
4	No event and lost to follow-up in any disposition page	Lost-to-follow-up
5	Death without an event	Death
6	No event and [EOS][a] present OR all EOT disposition pages of all drugs in a treatment arm say participant will not continue into any subsequent phase of the study] and no adequate post-baseline disease assessment	No adequate post-baseline disease assessment
7	No event and none of the conditions in the prior hierarchy are met	Ongoing without an event

[a] EOS here refers to completion of follow-up disposition page.

A listing for time to recurrence of low-grade disease will be provided.

### 6.2.2.9. Disease specific survival (Cohort A only)

Disease specific survival (DSS) is defined as the time from randomization to death resulting from bladder cancer, as assessed by the investigator.

$$DSS = [\text{date of death due to bladder cancer or censoring} - \text{date of randomization} + 1]/30.4375$$

Participants last known to be alive will be censored at the date of last contact.

The treatment effect will be estimated using a Cox's Proportional Hazard model stratified by randomization strata to calculate the hazard ratio for DSS between each experimental arm and Arm C.

Kaplan-Meier estimates (product-limit estimates) will be presented by treatment arm together with a summary of associated statistics including the median DSS time with 2-sided 95% CIs. DSS rates at 12, 24, 36, 48, 60, 72, and 84 months will be estimated with corresponding 2-sided 95% CIs. The CIs for the median will be calculated according to Brookmeyer and Crowley (1982) and the CIs for the survival function estimates at specific time points will be derived using the log-log transformation according to Kalbfleisch and Prentice (2002) (with back transformation to a CI on the untransformed scale). The estimate of the standard error will be computed using Greenwood's formula. A Kaplan-Meier plot for disease specific survival will be generated.

Reasons for censoring will be summarized according to the categories in Table 22 following the hierarchy shown.

**Table 22. DSS Censoring Reasons and Hierarchy**

Hierarchy	Condition	Censoring Reason
1	Death due to reasons other than bladder cancer	Cause of death other than bladder cancer*
2	No event and [withdrawal of consent date $\geq$ date of randomization]	Withdrawal of consent
3	No event and [lost to follow-up in any disposition page OR data cut-off date – last contact date $>$ 365 days]	Lost to follow-up
4	No event and none of the conditions in the prior hierarchy are met	Ongoing without an event

\*Reasons other than disease under study on the Death Details CRF page

A listing for disease specific survival will be provided.

### 6.2.2.10. Time to cystectomy (Cohort A only)

Time to cystectomy is defined as time from 'start date' to cystectomy. Participants without a cystectomy will be censored at death date or last date known to be alive.

The treatment effect will be estimated using a Cox's Proportional Hazard model stratified by randomization strata to calculate the hazard ratio for time to cystectomy between each experimental arm and Arm C.

Kaplan-Meier estimates (product-limit estimates) will be presented by treatment arm together with a summary of associated statistics including the median time to cystectomy with 2-sided 95% CIs. Time to cystectomy rates at 6, 12, 18, 24, 30, 36, 42, and 48 months will be estimated with corresponding 2-sided 95% CIs. The CIs for the median will be calculated according to Brookmeyer and Crowley (1982) and the CIs for the survival function estimates at specific time points will be derived using the log-log transformation according to Kalbfleisch and Prentice (2002) (with back transformation to a CI on the untransformed scale). The estimate of the standard error will be computed using Greenwood's formula. A Kaplan-Meier plot for time to cystectomy will be generated.

Reasons for censoring will be summarized according to the categories in Table 23 following the hierarchy shown.

